NSCLC (non-EGFR, ALK, or ROS1 mutated)	
Squamous or non-squamous: Chemotherapy ± Portrazza or Avastin {Eli Lilly and Company 2015; Genentech Inc. 2016; Patel 2013} ORR 33%
 
 • PFS 6 mo. • OS 12-13 mo. 
Keytruda (≥50% PD-L1+ only) {Merck & Co Inc 2017}
 
 • ORR 45% • PFS 10 mo. • OS >19 mo. 
Non-squamous: Keytruda + chemotherapy) {Merck & Co Inc 2017}
 
 • ORR 55% • PFS 13 mo. • OS >21 mo. 	
Squamous or non-squamous: Opdivo {Bristol-Myers Squibb Company 2017a}
 
 • ORR 27-56% • PFS 2-4 mo. • OS 9-12 mo. 
Keytruda (≥ 1% PD-L1+ only) {Merck & Co Inc 2017}
 
 • ORR 18-19% • PFS 4 mo. • 10-13 mo. 
Tecentriq {Genentech, Inc. 2017} ORR 22%
 
 • OS 13 mo. 	Unused first- and second-line therapies, depending on prior treatment and patient's resistance profile
TNBC (efficacy data for all breast cancer subtypes since data specific to TNBC data not available)	
Combination chemotherapy {Hospira, Inc. 2014; Eli Lilly and Company 2014}
 
 • ORR 41-45% • OS 15-19 mo. 	
Chemotherapy {Bristol-Myers Squibb 2007; Genentech Inc. 2015}
 
 • ORR 12-26% 	
Chemotherapy {Eisai Inc. 2016}
 
 • OS 13 mo.
Melanoma (non-BRAF mutated)	
Opdivo + Yervoy {Bristol-Myers Squibb Company 2017a; Bristol-Myers Squibb Company 2017b}
 
 • ORR 50% • PFS 11.5 mo. 	
Opdivo {Bristol-Myers Squibb Company 2017a}
 
 • ORR 34% • PFS 5 mo. • OS > 15 mo. 
Keytruda {Merck & Co Inc 2017}
 
 • ORR 33% • PFS 4 mo. • OS > 20 mo. 	Unused first- and second-line therapies, depending on prior treatment and patient's resistance profile

Gastric cancer	Combination chemotherapy {Hospira, Inc. 2017; Luo 2011; MacDonald 1980} 
 • ORR 37-44% • PFS 6-7 mo. • OS 6-11 mo. 	Ramucirumab + chemotherapy {Eli Lilly and Company 2017} 
 • ORR 28% • PFS 4.4 mo. • OS 9.6 mo. MSI-H: Pembrolizumab {Merck & Co Inc 2017} 
 • ORR 56%. 	Pembrolizumab (PD-L1+ only) {Merck & Co Inc 2017} 
 • ORR 13%

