1.6.4. JTX-2011 in Combination with Pembrolizumab

Based on clinical data with pembrolizumab, the risk of acute inflammatory reaction due to cytokine release is very low. Severe or life-threatening infusion-related reactions, including hypersensitivity and anaphylaxis, have been reported in 6 (0.2%) of 2799 patients treated with pembrolizumab. A risk of immune-mediated adverse reactions has occurred with clinical use of pembrolizumab, including (but not limited to): pneumonitis, colitis, hepatitis, endocrinopathies, nephritis and renal dysfunction and skin adverse reactions {Merck 2014}. No clinical or preclinical studies have been conducted to evaluate the safety of pembrolizumab in combination with JTX-2011. The mechanism of action and safety profile of pembrolizumab is very similar to that of nivolumab, which has been administered safely to subjects with advanced solid tumors in Study JTX-2011-101.

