 - e) C05: Endometrial cancer that is locally determined to have a mismatch repair deficiency (dMMR) as determined by immunohistochemical complete loss of expression (absence of nuclear immunoreactivity) of at least one of the mismatch repair genes MSH2, MSH6, MLH1 and PMS2, or to be microsatellite instability-high (MSI-H) by polymerase chain reaction (PCR) (*closed to enrollment*);

- f) C06: TNBC that is immunotherapy naïve [negative per ASCO/CAP guidelines for estrogen receptor (ER) protein expression and progesterone receptor (PR) protein expression (< 1% of tumor cell nuclei are immunoreactive), and negative for human epidermal growth factor receptor (HER2) protein expression by IHC assay (0 or 1) or by fluorescence *in situ* hybridization (FISH)];
- g) C07: Mesothelioma that is immunotherapy naïve;

6) Part D:

- a) D01: HNSCC that progressed on or after at least 2 months of a prior PD-1 inhibitor;
- b) D02: NSCLC that progressed on or after at least 2 months of a prior PD-1 inhibitor; Subjects with EGFR or ALK genomic tumor aberrations must have progressed on or after FDA approved therapy for these aberrations;
- c) D03: TNBC [negative per ASCO/CAP guidelines for estrogen receptor (ER) protein expression and progesterone receptor (PR) protein expression (< 1% of tumor cell nuclei are immunoreactive), and negative for HER2 protein expression by IHC assay (0 or 1+) or by FISH];
- d) D04: Melanoma that progressed on or after at least 2 months of a prior PD-1 inhibitor (*closed to enrollment*);
- e) D05: gastric cancer, including subjects with cancer of the gastro-esophageal (G-E) junction. Subjects with HER2 over-expressing tumors must have progressed on or after FDA approved therapy for HER2 over-expressing metastatic gastric or gastroesophageal junction adenocarcinoma;
- f) D06: Endometrial cancer that is locally determined to have a dMMR as determined by IHC complete loss of expression (absence of nuclear immunoreactivity) of at least 1 of the mismatch repair genes MSH2, MSH6, MLH1 and PMS2, or to be MSI-H by PCR (*closed to enrollment*);
- g) If a PD-1 or PD-L1 inhibitor is approved for treatment of TNBC during enrollment of this study, eligibility for subjects within that indication will require progression during or after prior treatment with the approved PD-1 or PD-L1 inhibitor;

7) Part F:

- a) F61: mCRPC that has progressed on or after treatment with at least 1 prior standard of care therapy;

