5.8. Part H (JTX-2011 in Combination with Pembrolizumab Combination Phase 2)

Part H will include six (6) cohorts in the indications listed below, dosing JTX-2011 at q3w in combination with pembrolizumab in Cohorts H31-H35 and q6w in combination with pembrolizumab in Cohort H64. Approximately 15 subjects will be enrolled in Cohorts H31-H33 and H35. Cohorts H34 and H64 are expansion cohorts and will each enroll approximately 49 subjects. All subjects must be immunotherapy naïve:

q3w JTX-2011 + q3w Pembrolizumab

- H31: recurrent or metastatic HNSCC with disease progression on or after platinum-containing chemotherapy;
- H32: metastatic NSCLC that has high PD-L1 expression (TPS Score $\geq 50\%$) as determined by an FDA-approved test, with no EGFR or ALK genomic tumor aberrations;
- H33: metastatic or recurrent TNBC with ≤ 1 prior line of therapy in the metastatic or recurrent setting;

- H34: recurrent locally advanced or metastatic gastric or gastroesophageal junction adenocarcinoma, including adenocarcinoma of the lower esophagus with disease progression on or after 1 prior line of therapy, including HER2/neu-targeted therapy, if appropriate;
- H35: unresectable or metastatic MSI-H solid tumors that have progressed on prior FDA-approved treatment and who have no satisfactory alternative treatment options or MSI-H colorectal cancer that has progressed following treatment with a fluoropyrimidine, oxaliplatin, and irinotecan.

q6w JTX-2011 + q3w Pembrolizumab

- H64: recurrent locally advanced or metastatic gastric or gastroesophageal junction adenocarcinoma, including adenocarcinoma of the lower esophagus with disease progression on or after 1 prior line of therapy, including HER2/neu-targeted therapy, if appropriate

Pre-screening for ICOS will not be required. Subjects in Part H are required to have archival tumor and a fresh tumor biopsy during screening. In situations where archival tissue is not available or biopsies are not feasible (e.g., would expose the subject to unreasonable health risks), one or more of these requirements may be waived after discussion with the Medical Monitor.

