In **Part C**, **Part D**, **Part F** and **Part H** the preliminary efficacy signal, measured by the overall response rate (ORR), will be evaluated using a group sequential design with 1 interim look for futility. The following hypotheses $H_0: ORR \leq 0.08$ versus $H_1: ORR \geq 0.20$ will be tested with a 90% power at a 2-sided $\alpha=5\%$. As the first step, 15 (Part C) or 15 (Part D) or 15 (Part F) or 15 (Part H) subjects will be enrolled for each cohort in the current protocol. The anticipated total sample size for each cohort could be as large as 76 if warranted by the result obtained from the first 20 or 15 subjects. The following table lays out different scenarios based on the observed ORR from the first 20 or 15 subjects within each cohort:

Table 10: Operating Features of A Group Sequential Design with 1 Futility Interim Look at 20 or 15 Subjects with 90% Power and 2-sided $\alpha=5\%$.

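### The 8% null is too low for nivolumab cohorts open to PD-1-naive subjects, chiefly D05, and is not reconciled with the 13% null stated for the same parts

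*Protocol*

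**What the plan says.** Protocol 9.3 applies a single pair of hypotheses to every cohort of Parts C, D, F and H: "H_0: ORR \leq 0.08$ versus $H_1: ORR \geq 0.20$ will be tested". It attaches operating characteristics ("will be tested with a 90% power at a 2-sided $\alpha=5"%) and a ceiling ("The anticipated total sample size for each cohort could be as large as 76"). It cites no source for 8% and does not separate monotherapy from combination, or PD-1-naive from PD-1-experienced cohorts.

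SAP 9.12 repeats the pair for Parts C and D. Its Table 9 gives the rule: stop at 0 responses in the first 15 (or 20) subjects, otherwise expand to 76, with more than 10 responses labelled as a p-value below 5%.

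A second design appears in the protocol synopsis and in SAP 5: expansion to about 49 subjects, with 80% power to rule out 13% in favour of 28%. In SAP 5 it sits in the paragraph on Parts C and D.

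On populations, protocol 4.1 requires D01, D02 and D04 to have progressed on a PD-1 inhibitor. It sets no such condition for "D05: gastric cancer, including subjects with cancer of the gastro-esophageal (G-E) junction", for D06 (MSI-H or dMMR endometrial cancer, now closed), or at present for D03 (TNBC), where one would apply only if a PD-1 or PD-L1 inhibitor were approved during enrolment. All Part D subjects receive nivolumab.

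Table 2 (protocol 1.3) lists two PD-1-alone rates for gastric cancer: 13% in the third line for "Pembrolizumab (PD-L1+ only) {Merck & Co Inc 2017"}, and 56% in the second line for "MSI-H: Pembrolizumab {Merck & Co Inc 2017"}.

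**The concern.** In a single-arm combination cohort, the null rate stands in for what the partner would achieve alone. Where subjects may be PD-1-naive and all receive nivolumab, beating 8% does not show that JTX-2011 added anything if nivolumab alone already exceeds 8%. A D05 result of 11 responses in 76 would carry a p-value label below 5% and could be read as a signal for the combination, when the partner could explain it.

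The plan also states two different nulls covering the same cohorts. Only the 8% design comes with a response boundary, so it is the one an analyst would apply.

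**Working it through.** **1. Inputs.** Null 8%, alternative 20%, 90% power, two-sided 5%, N = 76 (protocol 9.3). Expand at ≥1/15, success at >10/76 (SAP Table 9). Second design: 13% versus 28%, 80% power, about 49 subjects (SAP 5, synopsis). Partner-alone proxy for D05: 13% (Table 2).

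**2. Reproduce the plan's figures.** One-sample score formula:

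N = [(z₀.₉₇₅·√(p0(1−p0)) + z_power·√(p1(1−p1))) / (p1−p0)]²

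- 8% versus 20%, 90% power: [(1.960·√0.0736 + 1.282·√0.16)/0.12]² = 75.7, so 76, as stated.
- Score test of 11/76 against 8%: (0.1447−0.08)/√(0.0736/76) = 2.08, two-sided p = 0.0375. For 10/76, p = 0.097. The cut-off of more than 10 reproduces.
- 13% versus 28%, 80% power: 47.8, so 48, close to the stated 49.

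The two designs are each coherent, but they are different designs.

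**3. Chance of meeting the SAP 9.12 rule with no JTX-2011 effect.** With true rate p, X1 ~ Bin(15, p) and X2 ~ Bin(61, p):

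- P(expand) = 1 − (1−p)^15. At 13%: 1 − 0.87^15 = 0.876.
- P(success) = Σ over x = 1 to 15 of P(X1 = x)·P(X2 ≥ 11−x).

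| True ORR, partner alone | Expand (≥1/15) | Expand, then ≥11/76 |
|---|---|---|
| 8% | 71% | 3.7% |
| 10% | 79% | 13% |
| 11% | 83% | 20% |
| 12% | 85% | 29% |
| 13% | 88% | 38% |

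Part of the 38% comes from the cut-off itself. The exact boundary against 8% (upper tail ≤ 0.025) is 12/76, and with it the figure at 13% is 27%. At N = 49 the exact 8% boundary is 9 responses, and the two-stage figure at 13% is 18%.

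**4. Boundary against 13%.** Smallest c with P(X ≥ c | 0.13) ≤ 0.025:

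- N = 49: c = 12 (tail 0.021; 11 gives 0.047).
- N = 76: c = 17 (tail 0.017; 16 gives 0.034).

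These agree with the Clopper-Pearson limits: the lower 95% limit is 13.3% for 12/49 (11.8% for 11/49) and 13.6% for 17/76 (12.5% for 16/76).

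**5. Power with those boundaries** (binomial upper tail, single stage):

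| True ORR | ≥12/49 | ≥17/76 |
|---|---|---|
| 20% | 26% | 35% |
| 28% | 76% | 89% |

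Requiring at least 1 response in the first 15 lowers each figure by less than one percentage point.

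**The case against.** **No formal testing.** SAP 3.3.1 disclaims hypothesis testing, SAP 7.10 and 7.11 rule out comparisons and significance, and expansion is optional. This limits the consequence to interpretation. But SAP 9.12 still says the hypotheses will be tested, claims 90% power and prints a p-value boundary, so the text needs correcting.

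**A 13% null already exists.** This stands. It means the plan does not rely on 8% alone, and for D05 the defect is two unreconciled designs, not the absence of a suitable null.

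**The 13% is a soft proxy.** This also stands. It is pembrolizumab in PD-L1+ third-line disease, while D05 uses nivolumab, is not PD-L1-selected and may include PD-1-experienced subjects. Protocol 1.6.4 supports the class comparison ("The mechanism of action and safety profile of pembrolizumab is very similar to that of nivolumab"), but not an exact rate. Hence the range from 10% to 13%.

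**The prior PD-1 subgroup is already listed.** It is in SAP 9.11.5, but only as optional.

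Three stronger readings are tempting and not supported:

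- *That the partner-alone rate is 13% to 56% in every affected cohort.* Table 2 gives no PD-1-alone rate for TNBC or endometrial cancer.
- *That D06 should have a 56% null.* That figure is pembrolizumab in MSI-H gastric cancer; moving it to nivolumab in endometrial cancer is extrapolation.
- *That Part H analyses are affected.* The mismatch is there in protocol 9.3: subjects had to be PD-1-naive ("All subjects must be immunotherapy naïve"), and Table 2 lists pembrolizumab at 16% in second-line HNSCC and 45% in NSCLC with PD-L1 of at least 50%. But SAP 4 says Part H never enrolled, and the rule of more than 10 in 76 is read from SAP Table 9, which covers Parts C and D.

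**Conclusion.** The concern holds for nivolumab cohorts that admit PD-1-naive subjects, and can be sized for D05 only. With no JTX-2011 effect, D05 would pass the SAP 9.12 rule 13% to 38% of the time if the partner alone gives 10% to 13%, against 3.7% under the plan's own null. This assumes that the Table 2 pembrolizumab rate stands in, at least roughly, for nivolumab in D05, and that the cohort expands to 76. For D03 and D06 the 8% null is unsupported, but the documents give no rate from which to size the error. The 8% null is reasonable for Part C and for D01, D02 and D04. Independently of the proxy, the 8%/20%/76 and 13%/28%/49 designs cannot both govern Parts C and D.

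The loose futility look is a separate matter: 71% of cohorts pass it even at a true 8%.

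**What to change.** - **SAP 9.12 and SAP 5:** state which design applies to which cohort. Keep 8% for Part C and for D01, D02 and D04. For D05 use the 13% null already in SAP 5.
- **D05 boundary:** restate it as at least 12/49 or at least 17/76 (exact, two-sided 5%), and read the Clopper-Pearson interval planned in SAP 9.11.1 against 13%.
- **D05 power:** delete the 90% claim and give the figures in step 5 of the working.
- **SAP 9.11.5:** make ORR by prior PD-1/PD-L1 therapy (yes/no) mandatory for D05.
- **D03 and D06:** state that meeting the 8% boundary is not evidence of a JTX-2011 contribution unless a partner-alone reference rate is justified.
- **Protocol 9.3:** note the same mismatch for Part H, for the record only; no analysis changes.

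Cost: SAP wording and recalculated boundaries, with no extra patients. The stated power for D05 becomes less favourable.

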9.4. Statistical Analysis

[figure not shown]
A high-level summary of major statistical analyses for the data collected through this protocol is included in this section. Details of planned statistical analyses and data presentations for safety and efficacy data will be specified in the Statistical Analysis Plan (SAP). Analysis of predictive biomarkers will be specified in the exploratory analysis plan (EAP). Jounce Biostatistics and Programming or designated clinical research organization (CRO) will perform the statistical analysis of the related data (SAP and EAP); SAS (Version 9.4, or higher) will be used to generate all statistical outputs (tables, figures, listings, and datasets). Analysis of other data (data other than safety or efficacy data) will be specified in the individual stand-alone analysis plans. All plans will be finalized and approved prior to the clinical database lock achieved for this study.

9.4.1. Determination of Sample Size

For Part A, Part B, Part E, and Part G, the choice of the number of subjects is based on the classical 3 + 3 design. The approximate sample size in the dose escalation cohorts in Part A will be 36 evaluable subjects assuming that 6 subjects are assigned at each of 6 planned dose levels. The approximate sample size of the dose escalation cohorts in Part B will be 24 evaluable subjects assuming that 6 subjects are assigned at each of 4 planned dose levels. The approximate sample size of the dose escalation cohorts in Part E will be 18 evaluable subjects assuming that 6 subjects are assigned at each of 3 planned dose levels. The approximate sample size of the dose escalation cohorts in Part G will be 12 evaluable subjects assuming that 6 subjects are assigned at each of 2 planned dose levels.

Approximately 8 additional subjects will be enrolled in safety/PK/PD expansion cohorts at each of 2 or more dose levels in Parts A (AP1, AP2) and B (BP1, BP2) to obtain additional safety and PK/PD data. Subjects may also be added if exploration of intermediate dose level(s) of JTX-2011 is warranted or if the SMC recommends adding additional subjects at a given dose level to further understand and clarify safety issues.

Approximately 120 subjects may be enrolled in Part C (approximately 15 in each cohort). Approximately 90 subjects may be enrolled in Part D (approximately 15 subjects per cohort). Approximately 30 subjects may be enrolled in Part F (approximately 15 subjects per cohort). Approximately 15 subjects may be enrolled in each Part H (assuming 3-6 will be enrolled in Part G). For Part C, Part D, Part F, and Part H, a group sequential design will be used to evaluate the preliminary efficacy of JTX-2011 or JTX-2011 in combination with nivolumab, ipilimumab or pembrolizumab, with an interim look for futility.

9.4.2. Analysis Set

All Subjects Set will include all subjects who have signed the informed consent and have subject numbers in the electronic clinical database.

The **Safety Population (SAF)** will include all subjects who have been treated with at least one dose of study drug (JTX-2011, nivolumab, ipilimumab, or pembrolizumab). The SAF will be the primary analysis set for all efficacy and safety analyses, unless otherwise specified.

Pharmacokinetic/Pharmacodynamic Analysis Set (PK/PD Set) will include all subjects who received at least one dose of the study drug and who provide at least one observation for at least one of the PK or PD endpoints without protocol violations that would be deemed by the trial pharmacokineticist to interfere with the PK or PD analysis.

Immunogenicity Analysis Set will include all subjects who received at least one dose of the study drug and provided one serum sample that could be successfully analyzed by both a screening and confirmatory validated ADA assay (for ADA analysis) or NAb assay (for NAb analysis).

9.4.3. General Considerations

All individual subject data for those who signed ICF and obtained subject numbers will be presented in data listings.

Unless otherwise specified, continuous endpoints will be presented by number of non-missing values, mean, median, standard deviation, minimum, and maximum values. Categorical endpoints will be presented by frequencies and percentages.

9.4.4. Patient Disposition

The number of subjects in each defined analysis set will be summarized. In the same summary table, subjects who completed study, or discontinued study early will be summarized with reasons for subjects' withdrawal (from treatment or follow-up) by frequencies and percentages.

9.4.5. Demographic and Baseline Characteristics

Demographic and baseline characteristics will be summarized based on SAF. Continuous endpoints will be summarized by N, mean, median, minimum, maximum, and standard deviation. Categorical endpoints (includes binary endpoints) will be summarized by frequencies and percentages per category.

9.4.6. Concomitant Medication

Medications used in this study will be coded by using the World Health Organization Drug Dictionary Enhanced (WHO-DDE) and categorized as the following:

- **Prior medication:** any medication that started before the first dose of study drug, regardless of when the medication ended.
- **Concomitant medication:** medication continued or newly received at or after the first dose of study drug through the end of treatment emergent period (defined in the SAP).
- **Post-treatment medication:** medication continued or newly received after the treatment emergent period.

A given medication can be classified as a prior, a concomitant, or a post-treatment medication; both prior and concomitant; both concomitant and post-treatment; or prior, concomitant, and post-treatment. If a medication has a missing or partially missing start/end date and it cannot be determined whether it was taken before the first dose, concomitantly, or beyond the treatment emergent period, it will be considered as prior, concomitant, and post-treatment.

For the SAF, prior medications and concomitant medications will be summarized descriptively by: 1) preferred name; and 2) anatomic class (ATC) level 1, ATC level 2, and preferred name. Post-treatment medications will be listed by subject.

9.4.7. Subject Adherence

For subjects in SAF, number of treatment cycles per patient will be summarized by frequencies and percentage of subjects who received each number of treatment cycles.

9.4.8. Safety Analyses

Assessment of safety will be performed for all subjects who receive at least one dose of study drug and for whom at least one post-dose safety observation is recorded (the Safety Population). Safety data that will be evaluated include DLTs, AEs/SAEs (including changes from baseline in physical examination findings), clinical laboratory results, vital signs, ECOG performance status, ECGs and any other pertinent results. Safety and tolerability endpoints will be summarized descriptively.

9.4.8.1. Adverse Events

Adverse events will be classified into standardized terminology from the verbatim description (Investigator term) according to the most recent version of the MedDRA adverse event coding dictionary at time of data analysis. Adverse events will be presented by Preferred Term nested within System Organ Class (SOC). Verbatim description and Preferred Term and SOC MedDRA-level terms for all AEs will be contained in the data listings of the Clinical Study Report for this protocol.

Adverse events will be summarized by the incidence of AEs/SAEs by body system and by preferred term. The incidence of AEs/SAEs will be based on the numbers and percentages of subjects with AEs/SAEs. Although a MedDRA term may be reported more than once for a patient, that patient will be counted only once in the incidence count for that MedDRA term. The severity of the AEs/SAEs and the relationship to the study drug will be summarized for each body system and preferred term by treatment group. Withdrawals due to AEs/SAEs will be summarized for each body system and preferred term.

AEs/SAEs will be classified based on the AE start date in relation to the first dose date as the following:

- Treatment-emergent AEs, defined as AEs that newly emerge, re-emerge or worsen on or after the first dose of study drug; all these AEs would have a start date on or after the first dose date of the study drug.
- Pre-treatment events, defined as AEs that newly emerge, re-emerge or worsen before the first dose of study drug; all these AEs would have a start date before the first dose date of the study drug.
- Post-treatment events, defined as AEs that newly emerge, re-emerge or worsen after the treatment emergent period (defined in SAP) of the study drug; all these AEs would have a start date after the last day of the safety window of the study drug.

Only treatment emergent AEs will be summarized. All adverse events will be included in all AE data listings with flags indicating treatment emergent, pre- or post-treatment.

In consideration of the varying durations of treatments, the incidence of treatment emergent adverse event will be presented in the following ways, as appropriate, (1) by cohort and overall; (2) by time interval, depending on the distribution of duration of treatment, e.g., by 1-, 3-, 6-, or 12-month intervals from start of therapy; and (3) by event rate per patient year (i.e., # of events per patient per year).

